Note. ¹For Go to R33, at least 2 of the 3 primary mechanism indicators must change and at least one of the secondary indicators must change. For

Second, at least one of the secondary measures must show a moderate effect ($d = 0.50$) from pre- to post-treatment. We included measures of each of the targets, as they are conceptualized as interrelated parts of a "stuck" system. For "Go" to an R01 after the R33, in addition to target engagement, primary outcomes of PTSD and depression must show clinically meaningful gains (e.g., Barth et al., 2016; Cusak et al., 2016).

R33 PATH Refinement. Beyond examining outcome data from the R61, we will: 1) conduct interviews with standardized questions with 20% of patients, selecting those with small and large gains on therapeutic targets; 2) conduct a feedback session with therapists to identify aspects of the manual that need refinement; and 3) examine booster session data regarding whether additional sessions are needed for the R33. The interview guides will be submitted as through a modification before they are conducted.

Data Analysis Plan

Directions: Describe the data analysis plan, including any statistical procedures. If applicable, provide a power analysis, describe primary and secondary study endpoints including safety endpoints.

General Analytic Strategy

For Specific Aims 1–3, we will use random effects models, a specific application of general linear mixed models (GLMMs) that helps to address common issues with longitudinal clinical treatment data, including missingness, serial correlation, and time-varying covariates (e.g., Gallop & Tasca, 2009). These models allow for person-specific deviations from overall mean time effects and are robust to missing data, using maximum likelihood estimation in cases of ignorable non-response. This analytic approach allows for initial modeling of different covariance structures, as well as non-linear time transformations that are especially useful when between-assessment intervals are not consistent across time. For Aim 3, mediation will be tested using the product of coefficients method with bootstrapped standard errors (MacKinnon, 2009) and based on a lagged mediation design (e.g., Hofmann, 2006). This approach addresses the need for temporal precedence of predictor to outcome and accounts for change between time points of a target DV. Analyses involving secondary metrics (i.e., PTCI, BADS, SHAPS) will shift to a more conservative GLM framework.

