Our approach to power analyses aims to balance pragmatic factors with analytic considerations. We focus primarily on Specific Aim 1 (R61) and Specific Aim 2 (R33). Primary analyses for both aims will involve random effects models; however, because it is difficult to accurately estimate covariance structures of such models, *a priori* power or sample size estimations have limited value. Fang (2006) has shown that ideal sample sizes often far exceed clinical resources for conventional trials, whereas other studies have shown that small sample sizes do not bias estimates of fixed effects (e.g., Bell et al., 2008). Accordingly, we frame our power calculations in line with GLM models that mirror the primary tests and hypotheses of our more complex random effects/GLMM models. In general, estimates were calculated based on $\alpha = .05$ and power $(1 - \beta) = .80$, using intent-to-treat, repeated-measures designs (e.g., paired t-tests). Power calculations were completed using G*Power (Faul et al., 2007). For Aim 1, with an estimated pre-post effect size of $d = 0.60$ (one-tailed tests), we are well-powered with a sample of 45. In fact, for a sample size of 45, an alpha of .05, and power of .80, we will be able to detect a small to moderate effect size of .38. For Aim 2, we based power estimates on a primary comparison of time by treatment interaction in an RMANOVA model. For a five time points, two groups, RMANOVA with a correlation of $r = .70$

between measures, we are well powered to detect treatment X time small effect size of .07 with 67 patients per treatment. For Specific Aim 3, using Monte Carlo simulations in MPlus 6.0 (Muthen & Muthen, 2002) with the same alpha, power, and sample size of at least 67 per condition, we are adequately powered to detect an indirect effect size as small as $d = .50$.

Specific Aim 1: Engage Targets (R61)

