We will examine whether PATH alters therapeutic targets in comparison to PMR. Primary dependent variables are Affective Updating, BATs, PRT. Secondary dependent variables are PTCI, BADS, and SHAPS. We will compare the main effect of treatment (PATH or PMR) over time separately in each of three models. These models will estimate the effects of treatment on both the level of the target at 3-month follow-up and change over time (slope). Random intercepts and random coefficients for time-varying covariates (e.g., time) will be specified, if the model fit is better than a fixed effects model. For example, $y_{ik} = \beta_0 + \beta_1 \text{Time}_{ik} + \beta_2 \text{Treatment}_{ik} + \beta_3 (\text{Treatment}_{ik} \times \text{Time}_{ik}) + v_{0i} + v_{1i} \text{Time}_{ik} + \epsilon_{ik}$ where Treatment represents a dummy-coded effect (Group = 0 for PATH, 1 for PMR), i=subject, k=time, and y = DV of interest. We hypothesize that differences will emerge between PATH and PMR specifically for Affect Updating, BAT, and PRT. For secondary measures, we will use the GLM approach above in an ANCOVA-like design to test the interaction of treatment and time.

Specific Aim 3: Linking Changes in Targets to Changes in Stressor-related Symptoms (R33):

We will examine whether changes in target mechanisms (pre- to post-) predict improvement in PTSD (PSS-I) and depression (QIDS-C) at pre-, mid, post-, 1-, 3-month follow-up. In GLMs, we will evaluate targets from pre- to post-treatment and at 3-month follow-up, with corresponding metrics to assess change in symptoms (PSS-I, QIDS-C). In the GLMs, treatment will predict changes in symptoms from pre- to post-treatment (controlling for baseline levels) and pre- to follow-up. GLMMs will be conducted as above, and treatment will be used to predict levels and change in symptoms. Next, in GLMs, we will

predict pre-post change in target mediators (unproductive processing, avoidance, reward deficits) from treatment (A path) and follow-up outcomes from the mediator (B path), controlling for treatment and baseline symptoms. GLMM will test for mediation by predicting the mediator at all time points from treatment, and the outcome at all time points from the mediator, controlling for treatment. Similar analyses will be used for secondary measures.

Specific Aim 4: Feasibility and Dropout/Acceptability of PATH Intervention (R61/R33):

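### The Aim 3 GLM mediation uses pre-post target change without adjusting for the pre-treatment target; adding that covariate is a cheap improvement that guards against an attenuated mediator-outcome path

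*Combined protocol and SAP*

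**What the plan says.** The Specific Aim 3 section of the Data Analysis Plan has two mediation analyses.

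- **GLM.** The A path will "predict pre-post change in target mediators (unproductive processing, avoidance, reward deficits) from treatment (A path"). The B path predicts "follow-up outcomes from the mediator (B path), controlling for treatment and baseline symptoms". Neither equation names the pre-treatment value of the target.
- **GLMM.** In parallel, "GLMM will test for mediation by predicting the mediator at all time points from treatment, and the outcome at all time points from the mediator", with treatment also in the model. This uses repeated mediator values, not a change score.

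Under General Analytic Strategy, "For Specific Aims 1–3, we will use random effects models", but "Analyses involving secondary metrics (i.e., PTCI, BADS, SHAPS) will shift to a more conservative GLM framework". The Aim 3 section ends by extending similar analyses to the secondary measures. The indirect effect is to be tested by product of coefficients with bootstrapped standard errors.

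Baseline adjustment appears nearby. The same Aim 3 paragraph adjusts symptom change for baseline symptom level, and the dosing and timing paragraph of Aim 1 uses residualized target change. The general provision for covariates mentions gender and time since event as examples, but not the baseline target.

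**The concern.** A raw change score carries the pre-treatment value with a negative sign. If follow-up symptoms depend at least partly on where the target ends up, the pre-treatment part of the change score acts as noise in the B path and pulls its coefficient toward zero. The indirect effect shrinks with it. In the A path, randomization keeps the treatment contrast unbiased, but baseline variance stays in the residual and inflates the standard error.

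Aim 3 is the trial's test of mechanism. A GLM that understates the indirect effect could leave a real mechanism looking unsupported, when the trial already holds the data needed to avoid this.

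**Working it through.** **Inputs.** From the Power Analysis: at least 67 per condition (134 in total), alpha .05, power .80. Sidedness is not stated for Aim 3, so two-sided is assumed. A correlation of .70 between repeated measures is stated for the Aim 2 RMANOVA only; using it for the mediators is an assumption. The documents give no a path, b path, mediator retest correlation, pre/post SD ratio or target-symptom correlation for Aim 3.

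**The plan's own figure.** A detectable indirect effect of d = .50 is attributed to Monte Carlo runs whose path values are not given, so it cannot be reproduced. Some readings come close: a plain two-group comparison at d = .50 has noncentrality .5 × √(67/2) = 2.89 and about 82% power, and a joint test with a = b = .5 also gives 82%. Others do not: a = b = .707 gives 98%. The figure therefore cannot settle the inputs below.

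**A path.** With unit SDs and retest correlation r, the residual variance is 2(1−r) for raw change and 1−r² after adjustment. The SE ratio is √[(1+r)/2].

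- r = .5: √.75 = .866, a 13% cut (simulated: .172 to .150).
- r = .7: √.85 = .922, an 8% cut (simulated: about 7%).

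**B path, outcome following the post-treatment level.** Let s be the pre/post SD ratio, with baseline symptoms unrelated to the target. The unadjusted coefficient is b × (1−rs)/(1+s²−2rs).

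| s | r = .7 | r = .5 |
|---|---|---|
| 0.7 | .51/.51 = 1.00 | .65/.79 = .82 |
| 0.8 | .44/.52 = .85 | .60/.84 = .71 |
| 0.9 | .37/.55 = .67 | .55/.91 = .60 |
| 1.0 | .30/.60 = .50 | .50/1.00 = .50 |
| 1.1 | .23/.67 = .34 | .45/1.11 = .41 |

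At s = 1 the result is b/2 whatever r is. If baseline symptoms correlate with the pre-treatment target, and with the post-treatment target only through it, the factor at s = 1, r = .7 rises to .54, .61 and .73 for correlations of .3, .5 and .7. If they correlate equally with both, it stays at .50.

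**B path, intermediate truths.** If outcome depends on post − w × pre, with s = 1, the factor is (1+w)/2. For w = .5 this is .75, so b = .30 appears as about .23.

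**Power.** Set the adjusted B path at 80% power, so the noncentrality is 1.96 + 0.84 = 2.80. With s = 1 and a post-level truth, omitting the covariate divides this by √[2(1+r)]. At r = .7, 2.80/√3.4 = 1.52, or 33% power (about 30% simulated). At r = .7 with other inputs, unadjusted power is 54% (target-symptom correlation .7), 78% (s = .7), 18% (s = 1.1) and 8% (s = 1.25).

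**Joint test.** Simulation with n = 134, a = .5 SD, b = .30, r = .5 to .7, s = 1, target-symptom correlation 0 to .5 and an assumed outcome residual variance. Significance of both paths stands in for the bootstrapped product.

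| Outcome depends on | Unadjusted b; both significant | Adjusted b; both significant |
|---|---|---|
| Post-treatment level | .15–.18; 28–50% | .30; 77–85% |
| Post − 0.5 × pre | .23–.24; 59–68% | .30; 77–84% |

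**If only change matters.** Both models are unbiased. Adjustment multiplies the B-path noncentrality by √[(1+r)/2], so 80% power becomes 73% (r = .7), 68% (r = .5) or 62% (r = .3). From a higher start the loss is smaller: 91% to 86% at r = .7, and 98.5% to 95% at r = .5. In the joint test, the A-path gain reverses the loss at r = .5 (80% to 85%, and 78% to 83%) and limits it to 2 to 5 points at r = .7.

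**The case against.** The strongest reply is that Aim 3 is worded in terms of change: changes in targets are to predict improvement. If change itself drives outcome, the planned B path is unbiased and more efficient, and no passage favors a level model. This stands as a limit, but pure change is one special case. The adjusted model contains it and stays unbiased there, whereas the unadjusted model is attenuated at the intermediate truths shown.

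A second reply is that the GLMM gives the primary targets a mediation test free of the change score. This also stands, and it narrows the point. It does not remove it: the secondary measures move to GLM. The GLMM description also states no lag, while General Analytic Strategy promises a lagged mediation design; the GLM, with pre-post change predicting follow-up, is the test described that has that ordering.

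Third, exact halving needs equal SDs. Inclusion requires elevated symptom items on at least two of the three targets, which could narrow the baseline spread, and at r = .7 an SD ratio of .7 removes the attenuation. That is plausible but unknown, and a ratio above 1 makes matters worse.

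A reader might infer that the Aim 3 result as a whole is biased toward zero, that the B path is halved at any retest correlation, or that power falls to a definite range such as 33 to 53%. The documents support none of these. The GLM is not the only Aim 3 test. Halving needs a post-level truth, equal SDs and no help from baseline symptoms. The power figures depend on values the plan does not give. Even with adjusted B-path power fixed at 80%, a fall to about 53% goes with a path cut of about 27% (factor .73), not 50%.

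**Conclusion.** This is a cheap improvement, not an invalid analysis. As written, the Aim 3 GLM mediation omits the pre-treatment target from both paths. The loss of A-path precision follows whenever pre- and post-treatment values are correlated as assumed here: adjustment cuts the standard error by about 7 to 13% at r = .7 to .5 with equal SDs. Attenuation of the B path and the indirect effect is conditional. It occurs unless outcome depends purely on change or the pre-treatment SD is well below the post-treatment SD, and it reaches one half with equal SDs and an outcome that follows the post-treatment level.

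The simulated contrast of 28 to 50% against 77 to 85% shows how large the loss could be. It is not an estimate for this trial. The consequence is greatest for PTCI, BADS and SHAPS.

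**What to change.** In both Aim 3 GLM equations, for primary and secondary targets, add the pre-treatment value of the same target:

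- **A path:** post-treatment target (or change) on treatment and pre-treatment target.
- **B path:** follow-up symptoms on target change (or post-treatment target), treatment, baseline symptoms and pre-treatment target.

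Once the pre-treatment value is in the model, change and post-treatment level give the same treatment coefficient in A and the same mediator coefficient in B, so the choice between them no longer matters. Keep the unadjusted change-score model as a prespecified sensitivity analysis, and state the a path, b path, retest correlation and SD ratio behind the Aim 3 power figure.

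The cost is one already-collected covariate per equation. If outcome depends purely on change, B-path power falls by about 5 to 7 points at r = .7, and by more at lower r when it starts near 80% (12 points at .5, 18 at .3). The more precise A path offsets this partly or fully in the joint test.

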Specific Aim 2: Replication of Target Engagement (R33): In a randomized control trial ($N = 135$), we will examine whether PATH alters therapeutic targets from pre- to 3-month follow-up in comparison to PMR.

Specific Aim 3: Link Changes in Targets to Changes in Stressor-related Outcomes (R33): We will examine whether changes in therapeutic targets (pre- to post-) predict improvement in PTSD and depression symptoms (pre- to 3-month follow-up).

Specific Aim 4: Feasibility and Dropout/Acceptability of PATH (R61/R33): We will examine whether patients perceive PATH as helpful and complete/adhere to treatment, and therapist fidelity.

There is an urgent need to develop novel treatments, given the prevalence, impact, and cost of PTSD and MDD (e.g., Hoge & Chard, 2018). PATH is an innovative intervention that targets three interrelated, transdiagnostic processes that maintain stressor-related psychopathology. PATH's unique early and sustained focus on positive emotions could improve adherence and outcome, particularly in those with the reward deficits commonly seen in PTSD and MDD. Further, PATH's focus on positive emotions and "stuck" processing targets unique processes largely absent in current PTSD therapeutics. PATH is novel in applying exposure principles to depression, not just PTSD. This brief, positive, mechanistically precise, transdiagnostic treatment has the potential to improve treatment engagement and outcomes, identify clear therapeutic targets that predict better outcomes, and ultimately reduce the costly burden of stressor-related psychopathology.

We hypothesize that (1) those in PATH will have significant changes in the therapeutic targets, (2) those in PATH will show a greater change in therapeutic targets than those receiving Progressive Muscle Relaxation (PMR), (3) changes in therapeutic targets predict improvement in PTSD and depression symptoms, and (4) those in PATH will perceive the intervention as helpful and adhere to treatment.

Background

Directions: Describe the relevant prior experience and gaps in current knowledge describing how it will add to existing knowledge. Include any relevant preliminary data.

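### The Aim 3 mediation GLMM specifies no visit terms and does not separate within-patient change from stable differences, so its B path can be significant with no true target-symptom link

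*Combined protocol and SAP*

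**What the plan says.** All references are to the combined protocol and SAP.

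- **Aim (Objectives, Specific Aim 3).** The question is "whether changes in therapeutic targets (pre- to post-) predict improvement in PTSD and depression symptoms", so it concerns change.
- **Analysis (Data Analysis Plan, Specific Aim 3).** Three models are given in turn.
  - For arm effects on symptoms: "GLMMs will be conducted as above, and treatment will be used to predict levels and change in symptoms".
  - A GLM mediation, in which arm predicts the pre-post change in the target, and the target then predicts the follow-up outcome with arm and baseline symptoms as covariates.
  - A GLMM mediation, described only as "predicting the mediator at all time points from treatment, and the outcome at all time points from the mediator, controlling for treatment".
- **General Analytic Strategy (Aims 1–3).** Of the random effects models it says: "These models allow for person-specific deviations from overall mean time effects". Aim 3 mediation uses the "product of coefficients method with bootstrapped standard errors" and is "based on a lagged mediation design". The stated reason is: "This approach addresses the need for temporal precedence of predictor to outcome and accounts for change between time points of a target DV". The order of the lag and its covariates are not given.
- **Specific Aim 2.** The example equation has linear time and treatment-by-time. On random effects: "Random intercepts and random coefficients for time-varying covariates (e.g., time) will be specified, if the model fit is better than a fixed effects model".

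No section separates within-patient from between-patient variation in the target, and none says whether the GLM or the GLMM decides Aim 3.

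**The concern.** The only covariate named in the mediation GLMM is arm. Three things follow if it is fitted that way.

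1. Targets and symptoms that both improve over visits share a trend. With no visit term, the trend alone produces a B path.
2. A raw time-varying target carries each patient's general level as well as change. Patients who are worse on both scales throughout produce a B path with no change at all.
3. An arm effect on the target averaged over all visits includes pre-treatment, where randomisation makes the expected difference zero. This dilutes the A path.

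Aim 3 is meant to show which targets carry the benefit. A coefficient that mixes trend, level and change cannot show that, and nothing in the plan stops this model from supplying the headline mechanism result.

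**Working it through.** **The plan's own figure.** Power Analysis states that an indirect effect of d = .50 is detectable with at least 67 per condition. It cannot be rebuilt, because the a and b values are not given. As a bracket, a plain two-group d of .50 with 67 per arm has 82% power.

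**Inputs from the documents.** 67 per arm, five visits, correlation .70 between repeated measures (Power Analysis); target change d = .60 and symptom change d = .80 (Table 3).

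**Assumptions.** Improvement follows the profile 0, .5, 1, 1, 1 over the five visits. Tests are two-sided at .05, the model has a random intercept, and there is no dropout. Stable target and symptom levels correlate 0, .3 or .5.

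**Model as written.** Target_ik = α + a·Arm_i + u_i + e_ik. Symptom_ik = γ + b·Target_ik + c·Arm_i + v_i + e_ik. Indirect effect = a × b.

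**Step 1, shared trend (true b = 0).** The profile has mean .7 and variance (.49 + .04 + 3 × .09)/5 = .16. Within-patient covariance from the trend alone is .6 × .8 × .16 = .0768. Within-patient target variance is .30 × 4/5 + .36 × .16 = .2976. The spurious within-patient slope is .0768/.2976 = .258 (simulated .256). The random-intercept fit blends this with a zero between-patient slope and gives about .20. It is significant in 99.7% to 100% of trials. At .3/.4 SD the rate is 33% to 35%, at .2/.3 SD 13%, and at .1/.3 SD 7.7%.

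**Step 2, stable levels only (no change, correlation .5).** The between-patient slope is .5 × .70/(.70 + .30/5) = .35/.76 = .46, and the within-patient slope is 0. The blend is falsely significant in 68% of trials.

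**Step 3, A path and product.** The all-visit arm effect is .7 of the full effect: .7 × .40 = .28 (simulated .275). Its standard error is √(2 × .76/67) = .151, so z = 1.86 and power is about 46% (simulated 45%). The pre-to-post change contrast has standard error √(2 × 2 × .30/67) = .134, so z = .40/.134 = 2.99 and power is about 85%.

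Where b is almost always significant, false mediation occurs about as often as a is significant:

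- Arm difference .6 SD on the target and .8 SD on symptoms, stable correlation .3: z = .42/.151 = 2.79, or 80% (simulated 79%).
- Arm difference .5 SD on the target only: z = .35/.151 = 2.32, or 64% (simulated 65%).
- Arm differences .4/.5 SD: simulated 37% (43% in another run).
- Equal improvement in both arms: about 2% to 4%.

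**Step 4, does other text rescue the model?** False-positive rate for b with no true link, 600 trials per cell:

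| Model | Both arms improve .6/.8 | No change, stable r .3 | Both improve, stable r .5 | PATH moves each by .5 independently |
|---|---|---|---|---|
| As written | 99.7% | 30.5% | 100% | 99.5% |
| Linear time × arm (Aim 2 form) | 65.5% | 31% | 100% | 60% |
| Lagged target, no time | 65.3% | 30.3% | 100% | 60% |
| Split, no time | 100% | 6.0% | 100% | 100% |
| Visit × arm, no split | 5.0% | 30.5% | 71% | 4.0% |
| Visit × arm and split | 8.0% | 6.7% | 6.5% | 5.2% |
| Companion GLM | 6.0% | 5.5% | 6.5% | 6.0% |

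Simulation error is about 1 to 2 points. The linear-time figure in the first column depends on coding: about 66% with time in elapsed weeks, and about 29% with visits numbered in equal steps. Either way linear time leaves a plateau unmodelled. A lagged target plus prior symptoms, still without visit, gives 6.8% at .6/.8 SD but 97% at stable correlation .5.

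**Step 5, is visit plus the split enough?** No. If PATH moves target and symptoms independently, visit plus the split without arm-by-visit still gives 11% to 40%. Adding arm-by-visit to the outcome equation brings this to about 3% to 10%.

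**The case against.** The case for the plan has four parts.

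- **Time is not excluded.** The general strategy refers to mean time effects and a lagged design, and the Aim 2 equation contains time. A reader might infer from the Aim 3 sentence that the model will have no time term. The documents do not say so; they only fail to specify one. This limits the wording but does not rescue the model: the sentence that refers back to the earlier GLMMs concerns arm predicting symptoms, linear time cures neither fault, and the lag is undefined.
- **Aim 3 has a second analysis.** The change-score GLM matches the stated aim and holds its error rate (3% to 7.5% across runs). A reader might infer that Aim 3 as a whole cannot be answered. That is not supported.
- **The test is a × b, not b.** A reader might take the 100% as a false mediation rate. It is not: with equal improvement in both arms false mediation is about 2% to 4%. The protection disappears when PATH moves the target more than PMR, which is hypothesis 2 in Objectives.
- **The 100% case is demanding.** It gives both arms the full thresholds, although the PMR description says that treatment does not focus directly on the targets. It would be too strong to say that a link appears whenever both measures improve; the rate falls to 7.7% at .1/.3 SD.

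**Conclusion.** The point holds as a fault of specification in one of two Aim 3 mediation analyses. It should be fixed; it does not invalidate the aim. Fitted as written with no true link, the GLMM gives a false B path in about 100% of trials at .6/.8 SD improvement in both arms, about one third at .3/.4 SD, and about 68% when only stable levels correlate .5. False mediation runs at about 37% to 79% for arm differences from .4/.5 to .6/.8 SD, the larger case with a stable correlation of .3. The A path recovers only about 70% of the arm difference.

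The improvement profile, the stable correlations, the random intercept and the absence of dropout are assumptions. The documents give the sample size, the correlation of .70 and the .60/.80 thresholds. The two faults are separate: visit terms do not remove stable differences, and the split does not remove the trend.

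**What to change.** In the Specific Aim 3 text:

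1. Write out both mediation GLMM equations, with visit as a category and arm-by-visit in each.
2. Split the target into the patient's mean and the visit deviation from it, and use only the deviation coefficient as the B path.
3. State the lag and its covariates, so that the temporal order promised in General Analytic Strategy is kept. The corrected rates above are for same-visit deviations; repeat the simulation for the lagged version before finalising.
4. Take the A path from the arm-by-visit contrast for change from pre-treatment, not from the all-visit arm effect.
5. Name the change-score GLM as the primary mediation analysis and the corrected GLMM as supportive.

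The cost is SAP wording and a few model degrees of freedom. No new data are needed.
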